17. RISKS TO SUBJECTS

- *Describe any potential risks and discomforts to the subject (physical, psychological, social, legal, or other) and assess their likelihood and seriousness and whether side effects are reversible. Where appropriate, describe alternative treatments and procedures that might be advantageous to the subjects.*
- *Include risks to others, like sexual partners (if appropriate)*
- *Discuss why the risks to subjects are reasonable in relation to the anticipated benefits and in relation to the importance of the knowledge that may reasonably be expected to result.*
- *Describe the procedures for protecting against or minimizing any potential risks, including risks to confidentiality, and assess their likely effectiveness.*

Transcutaneous vagus nerve stimulation by the ear has the potential to cause temporary changes in hearing, pain at the site of stimulation, skin irritation or burns, and in rare occurrences, increases or decreases in heart rate as a result of activating the cervical vagus nerve via transcutaneous electrical stimulation of the ear. However, serious adverse events are unanticipated with tVNS, as there were no serious adverse device effects of implanted VNS or transcutaneous VNS in individuals with chronic stroke [8, 41].

Ear pain/discomfort occurs from stimulation of the sensory nerves innervating the ear. Activation of the sensory nerves correlates with the peak charge density applied to the innervated area. Consequently, during the stimulation period, we will monitor for discomfort and can adjust the charge intensity in real time to rapidly reduce the stimulation intensity and reduce the physical discomfort. This physical discomfort is not serious and the side effects are reversible.

Thermal burns at the stimulation site are due to excess power density through the electrode area. The FDA guidance for document for powered muscle stimulators (FDA document 2246) specifies a maximum power density at the electrode site of 250 mW/cm². The MIDI fabricated stimulator has a maximum power density of less than 100 mW/cm², which falls well below the guidance limit for thermal burns. A portable, battery-powered oscilloscope will be used to confirm peak current for the Roscoe device, and ensure that power density does not exceed this level.

Given the rare risk of heart rate changes occurring with tVNS, patients with known cardiac arrhythmias have been excluded from this study. Additionally, subjects will be continuously monitored during therapy. Any patient report of dizziness, lightheadedness, or nausea, which are associated symptoms with arrhythmia will result in immediate reduction in the stimulation intensity and/or cessation of stimulation and robotic intervention. A medical professional trained in basic life support (BLS) and will be present at the time of stimulation and afterwards. Additionally, appropriate medical equipment is available on site and the PI and other trained physicians are available on-call in the case of an emergency to further safeguard against risks.

There are no known risks associated with the use of robotic training for stroke rehabilitation. Some patients have pain in the shoulder after a stroke. Our experience has demonstrated a comparable incidence of shoulder pain in groups that were or were not treated by the robot.

There is also a risk of a breach of confidentiality if unauthorized individuals obtain access to protected health information. This risk will be minimized by securely storing all collected information and limiting access to study investigators only.

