7. ELIGIBILITY CRITERIA

- Describe the characteristics of the subject population, including their anticipated number, age, ranges, sex, ethnic background, and health status. Identify the criteria for inclusion or exclusion of any subpopulation.
- Explain the rationale for the involvement of special classes of subjects, such as fetuses, pregnant women, children, prisoners or other institutionalized individuals, or others who are likely to be vulnerable. You cannot include these populations in your research, unless you indicate such in the protocol
- Similarly, detail exclusionary criteria: age limits, special populations (minors, pregnant women, decisionally impaired), use of concomitant medications, subjects with other diseases, severity of illness, etc.

Inclusion Criteria:

- Individuals between 18 and 85 years of age
- First single focal unilateral supratentorial ischemic stroke with diagnosis verified by brain imaging (MRI or CT scans) that occurred at least 6 months prior
- Cognitive function sufficient to understand the experiments and follow instructions (per interview with Speech Pathologist or PI)
- Fugl-Meyer assessment 12 to 44 out of 66 (neither hemiplegic nor fully recovered motor function in the muscles of the shoulder, elbow, and wrist).

Exclusion Criteria:

- Botox treatment within 3 months of enrollment
- Fixed contraction deformity in the affected limb
- Complete and total flaccid paralysis of all shoulder and elbow motor performance
- Prior injury to the vagus nerve
- Severe dysphagia
- Introduction of any new rehabilitation interventions during study
- Individuals with scar tissue, broken skin, or irremovable metal piercings that may interfere with the stimulation or the stimulation device
- Highly conductive metal in any part of the body, including metal injury to the eye; this will be reviewed on a case by case basis for PI to make a determination
- Pregnant or plan on becoming pregnant or breastfeeding during the study period
- Significant arrhythmias, including but not limited to, atrial fibrillation, atrial flutter, sick sinus syndrome, and A-V blocks (enrollment to be determined by PI review)
- Presence of an electrically, magnetically or mechanically activated implant (including cardiac pacemaker), an intracerebral vascular clip, or any other electrically sensitive support system; Loop recorders will be reviewed on a case by case basis by PI and the treating Cardiologist to make a determination

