tVNS will target the left VNS in order to avoid cardiac side effects associated with right VNS stimulation. The tVNS device will be applied to the left ear using a pair of conductive silicone electrodes, with one electrode contacting the back of the ear and the other electrode on a spring loaded arm, contacting the cymba conchae. Patients will wear the tVNS device for the duration of each 1 hour robotic therapy session. During each session, patients will perform approximately 1000 shoulder/elbow flexion and extension movements and will receive stimulation during only the extensor movements, for a total of 300 stimulations per session. The tVNS current will be delivered during each extensor movement in single 500msec bursts with a frequency of 30Hz and a pulse width of 0.3msec. The current intensity will be individually adjusted to a level just below the patient's reported pain threshold, with amplitudes ranging from 0.1-5.0mA in steps of 100 μ A. The FDA guidance for document for powered muscle stimulators (FDA document 2246) specifies a maximum power density at the electrode site of 250 mW/cm². The MIDI fabricated stimulator has a maximum power density of less than 100 mW/cm², which falls well below the guidance limit for thermal burns. A portable, battery-powered oscilloscope will be used to confirm peak current (for the Roscoe device). These stimulation parameters are similar to parameters that have been demonstrated to be safe in several other tVNS clinical trials [8, 23, 34, 41].

To ensure participant tolerance of stimulation, current will be introduced at the lowest 0.1mA intensity and gradually increased to a level at which the patient just begins to report discomfort, or a maximum of 5mA. The device will then be immediately adjusted to an intensity just below the reported discomfort level, and will remain at this intensity for 10 seconds to confirm patient tolerance. This will be considered the maximum tolerated stimulation intensity threshold for the patient, and stimulation bursts during robotic therapy will then be administered at this level. This tolerability dose will be determined prior to every treatment session for all patients, and recorded in the stimulation tolerance monitoring log. Sham tVNS will have a comparable set-up to active tVNS, with 10 seconds of real current ramping to the maximally tolerated current intensity at commencement,

followed by a slow decrease to no current for the duration of the robotic therapy session.

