18. RESEARCH RELATED HARM/INJURY

- *Describe the availability of medical or psychological resources that subjects might need as a result of anticipated problems that may be known to be associated with the research.*
- *If the research is greater than minimal risk, explain any medical treatments that are available if research-related injury occurs, who will provide it, what will be provided, and who will pay for it.*

Since this study is considered minimal risk, physical injuries are not expected. However, if participants are injured from study participation, they will be provided treatment by Northwell Health. However, they or their insurance company will be responsible for the associated costs. No money will be given to participants.

Subjects will be continually monitored during the stimulation period, and will be in constant contact with a member of the research staff. The study can be immediately stopped at the subject's request.

In the case of a medical emergency, the PI and or other licensed physicians on site will be immediately summoned, and EMS may be contacted. Additionally, the Feinstein is equipped with necessary resuscitation equipment, including a code box, cardiac defibrillator, intravenous fluids, and supplemental oxygen. An EKG machine is also available at the CRC if needed. The PI or other licensed medical professional will be available to provide any and all medical treatments deemed necessary.

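### Section 17 says known arrhythmias are excluded, but Section 7 excludes only significant ones and leaves enrollment to PI review

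*Combined protocol and SAP*

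**What the plan says.** Section 17 names a cardiac risk of ear stimulation: "in rare occurrences, increases or decreases in heart rate as a result of activating the cervical vagus nerve". Its first answer to that risk is that "patients with known cardiac arrhythmias have been excluded from this study". The statement carries no severity qualifier and no exception.

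The exclusion list in Section 7 reads differently: "Significant arrhythmias, including but not limited to, atrial fibrillation, atrial flutter, sick sinus syndrome, and A-V blocks (enrollment to be determined by PI review". In the same list, implanted loop recorders get a two-person review: "Loop recorders will be reviewed on a case by case basis by PI and the treating Cardiologist to make a determination".

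On monitoring, Section 17 promises continuous observation during therapy and gives a symptom-based action: "Any patient report of dizziness, lightheadedness, or nausea, which are associated symptoms with arrhythmia will result in immediate reduction in the stimulation intensity", or cessation. Section 18 adds: "Subjects will be continually monitored during the stimulation period, and will be in constant contact with a member of the research staff". Section 11 sets the current before each session: "This tolerability dose will be determined prior to every treatment session for all patients, and recorded in the stimulation tolerance monitoring log". It also places the electrode on the left ear, expressly to avoid the cardiac effects of right-sided stimulation.

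**The concern.** Section 17 is where the board learns how the heart-rate risk is minimized; its template asks for the protective procedures and their likely effectiveness. A board member who reads that section alone would conclude that nobody with a known arrhythmia will be stimulated. Screening staff who follow Section 7 could enroll such a patient without deviating from the protocol. Either the safety statement or the eligibility rule needs to change.

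A lesser matter sits beside it. The continuous monitoring is offered in the cardiac paragraph, but no cardiac parameter is named, and the stated cardiac action waits for the patient to report a symptom. The protocol itself expects some subjects with cognitive impairment (Section 26) and notes that mild cognitive dysfunction or aphasia can be hard to recognize (Section 23). Section 7 does require enough cognition to follow instructions, which limits this worry without removing it.

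**Working it through.** The plan gives no figure on this point, so the check is mainly a comparison of texts.

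1. **Scope.** Section 17 covers every known arrhythmia, without exception. Section 7 covers significant arrhythmias, gives four examples in an open-ended list, and leaves enrollment to the PI.

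2. **The PI-review note.** It can be read in two ways.
   - *The PI may admit a patient who has a listed arrhythmia.* Then a patient with atrial fibrillation or A-V block can be enrolled.
   - *The PI only judges whether an arrhythmia is significant.* Then a patient whose known arrhythmia is judged not significant can be enrolled.

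   Section 17 is untrue as written on both readings. It would be true only if every known arrhythmia counted as significant and the note had no effect. Neither is stated.

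3. **Comparison within Section 7.** Loop recorders go to the PI and the treating cardiologist. Arrhythmias go to the PI alone.

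4. **Exposure of a patient so enrolled.** Section 11 gives 300 stimulations per session and 9 sessions, so 300 x 9 = 2,700 bursts in the active arm. A sham patient receives only the titration current and a 10-second ramp at the start of each session.

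5. **Heart-rate measurement.** Sections 10, 11 and 15 to 18 were read for any planned pulse, ECG or vital-sign reading, or any limit on one. None is named. Titration is bounded by reported discomfort or 5 mA. The EKG machine in Section 18 is listed with the emergency resources, for use if required.

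6. **Workload of two pulse readings per titration.**
   - All 36 subjects: 36 x 9 = 324 titrations; 324 x 2 = 648 readings.
   - Target of 15 per group: 30 x 9 = 270 titrations; 270 x 2 = 540 readings.
   - The documents give no time per reading. Assuming 15 to 60 seconds, two readings take 0.5 to 2 minutes per session. For 648 readings the total is 648 x 15 / 3600 = 2.7 hours to 648 x 60 / 3600 = 10.8 hours over the trial.

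**The case against.** The strongest reply has three parts.

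*It is loose wording, and PI discretion is normal.* Discretion over eligibility is defensible, and one of the fixes keeps it. But Section 17 does not disclose it, and presents the exclusion as complete.

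*The cardiac risk is already handled in proportion.* The plan calls the risk rare, the device non-significant risk and the study minimal risk. Section 11 reports no related serious adverse events in tVNS trials of 24, 30 and 7 patients, or in the site's own use of the device. Left-side targeting, symptom-triggered reduction or cessation, BLS-trained staff, on-call physicians, a defibrillator and an EKG machine are all in place. This stands. It is why the pulse proposal is optional: the documents do not show its absence to be an error.

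*Pulse readings would be awkward and incomplete.* A reading of 15 seconds or more does not fit the 10-second hold at treatment intensity, so the readings should come before and just after the titration. Discomfort at the top of the ramp may itself move the pulse, and readings at titration say nothing about the therapy hour. These limits also stand.

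Two stronger inferences should be resisted. A reader might take "during the stimulation period, we will monitor for discomfort and can adjust the charge intensity in real time" to mean that discomfort is the only thing watched. That sentence belongs to the paragraph on ear pain; the cardiac paragraph makes its own promise of continuous monitoring, and the fair criticism is that its parameter is unspecified. A reader might also take the visit table's silence on vital signs as proof that none are taken. The table is not exhaustive: the per-session tolerance questionnaire has no row in it, and the content of the first visit's medical screening is not described.

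**Conclusion.** The inconsistency between Sections 7 and 17 is real, and Section 17 is wrong as written. It bears on any candidate with a known arrhythmia. How many there would be among the 36 cannot be derived from the documents, so no rate or risk figure is offered.

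The conclusion assumes that Section 7 is the rule applied at screening and that no stricter rule operates elsewhere. Section 20 mentions a pre-screening checklist but does not give its contents.

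A reader might infer that patients with atrial fibrillation or A-V block will be enrolled, or that the trial has no cardiac protection. The documents support neither. The PI note permits, on one reading, what it does not require, and several cardiac safeguards are described. The unnamed cardiac parameter is a secondary point that justifies a suggestion only.

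**What to change.** **Preferred.** Exclude the four listed arrhythmias outright in Section 7. For any other known arrhythmia, require case-by-case agreement of the PI and the treating cardiologist, as loop recorders already do. Put the same rule in Section 17. Possible wording for both: *Patients with atrial fibrillation or flutter, sick sinus syndrome or A-V block are excluded; a patient with any other known arrhythmia may enter only if the PI and the treating cardiologist both agree.* This also says who decides on unlisted arrhythmias.

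**Alternative.** Keep the discretion in Section 7, add the treating cardiologist's input, and correct Section 17 to say that patients with known arrhythmias may be enrolled after that review.

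**Cost.** Either route changes a few words and adds cardiologist input for some candidates. The preferred route may add screen failures, whose number cannot be derived from the documents. Visits, target sample size and endpoints stay the same.

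**Optional.** In both arms, take a resting pulse before and just after the pre-session titration, write both in the existing tolerance log, and have the PI set in advance a limit that leads to reducing or stopping stimulation. The documents supply no value for that limit, so none is proposed here. The workload is the 648 readings (540 with 15 per group) worked out above. This supplements left-side targeting, the symptom trigger and emergency cover without replacing any of them, and it would not measure heart rate during therapy.

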18. RESEARCH RELATED HARM/INJURY

- *Describe the availability of medical or psychological resources that subjects might need as a result of anticipated problems that may be known to be associated with the research.*
- *If the research is greater than minimal risk, explain any medical treatments that are available if research-related injury occurs, who will provide it, what will be provided, and who will pay for it.*

Since this study is considered minimal risk, physical injuries are not expected. However, if participants are injured from study participation, they will be provided treatment by Northwell Health. However, they or their insurance company will be responsible for the associated costs. No money will be given to participants.

Subjects will be continually monitored during the stimulation period, and will be in constant contact with a member of the research staff. The study can be immediately stopped at the subject's request.

In the case of a medical emergency, the PI and or other licensed physicians on site will be immediately summoned, and EMS may be contacted. Additionally, the Feinstein is equipped with necessary resuscitation equipment, including a code box, cardiac defibrillator, intravenous fluids, and supplemental oxygen. An EKG machine is also available at the CRC if needed. The PI or other licensed medical professional will be available to provide any and all medical treatments deemed necessary.

19. POTENTIAL BENEFIT TO SUBJECTS

- *Explain what benefits might be derived from participation in the study, noting in particular the benefit over standard treatment (e.g. a once-a-day administration instead of four times a day, an oral formulation over an IV administration).*
- *Also state if there are no known benefits to subjects, but detail the value of knowledge to be gained*

The potential benefit of the proposed study is to develop a tool to augment conventional rehabilitation methods and improve motor recovery after stroke.

20. PROVISIONS TO PROTECT PRIVACY INTERESTS OF SUBJECTS

- *Describe the methods used to identify potential research subjects, obtain consent and gather information about subjects to ensure that their privacy is not invaded.*
- *In addition consider privacy protections that may be needed due to communications with subjects (such as phone messages or mail).*

Eligible participants will be recruited by Northwell Health clinician's in the Departments of Physical Medicine and Rehabilitation, Neurology, and Outpatient Stroke Rehabilitation at NSUH, LIJMC, GCH, SSH, Transitions of Long Island, and STARs Outpatient Rehabilitation Center. These clinicians will identify potential study participants, and either: 1.) provide the patient with the study coordinator's contact information or 2.) provide the patient's contact information to study personnel.

Investigators may contact (or be contacted by) a potential subject or subject's LAR/next-of-kin by telephone or email to discuss participation in this research protocol. The investigator will explain the goals and the risks of participating in this research study and the requirements of participation. If the subject/LAR/next-of-kin expresses interest in the study, the investigator will also review a pre-screening checklist, and schedule a meeting with the patient-subject. We will inform the patient that it is possible if they come in for the meeting, s/he may not be eligible for this study. If the subject is interested in participating in the study and has obtained a brain scan within the health system that is accessible through EMR, we can review that scan prior to the meeting if the subject provides verbal consent. Review of brain scans will occur in the interest of expediting determination of study candidacy, as many of our study participants have significant mobility impairments and prescreening brain scans may prevent excess hardship/travel to study site for ineligible subjects.

During the initial evaluation or screening visit, the investigator will verify the patient's candidacy and provide the subject/LAR/next-of-kin with all the

information contained in the written consent form, including a discussion of the risks/benefits of the study and the study schedule. The investigator will answer any questions regarding the research and give the subject/LAR/next-of-kin ample time to consider participation in the study. Following this discussion, the potential participant and/or their LAR/next-of-kin will be asked to provide consent to participation. Upon signing, the subject/LAR/next-of-kin will be provided with a copy of the consent.

In the event that a subject and/or LAR/next of kin arrives for the first evaluation and then requests to take the consent form home for review prior to signing it, minimal risk clinical measures of the subject's upper extremity function may still be collected during the initial study visit, prior to the signing of the consent, in order to reduce the burden on the disabled subject and their family who would otherwise be required to come for an additional study visit. If that subject and/or their LAR/next of kin then decline further participation in the study, the data for that subject's first evaluation will be destroyed.

In order to protect their confidentiality, subjects will be assigned a study ID number. The participant will then be referenced by that number. This identifiable information will be located on the HIPAA-compliant database, REDCap, and in hard-copy paper charts, which will be stored in a locked file cabinet. The study's de-identified data may be shared to facilitate study conduct such as data analysis. In addition, all study data will be securely maintained with access limited to investigators and authorized individuals only.

